Study Title: Internet-Behavioral Cough Suppression Therapy

Clinicaltrials.gov identifier: NCT05770401

Document date: 04/07/2025

Study Protocol

Background

Refractory chronic cough (RCC), defined as a chronic cough that has not responded to medical guideline-based treatment for the most common causes of cough, affects millions of people annually (Chung & Pavord, 2008; Song et al., 2015). Behavioral cough suppression therapy (BCST) provided by voice and upper-airway specialized speech-language pathologists is a highly efficacious treatment for RCC (Yi et al., 2024) but is underutilized (Chamberlain et al., 2015; Slovarp et al., 2021). For patients with RCC living in rural areas, the lack of BCST providers combined with accessibility barriers compound this issue (Towey, 2012, Meit et al., 2014). Innovations in treatment modality are needed to increase the availability and accessibility of BCST. Internet-based interventions offer an avenue to connect more patients with specialized healthcare services.

Objective

The primary aim of this study was to investigate the efficacy of internet-based behavioral cough suppression therapy (IBCST) compared to a healthy-lifestyle education control in patients with RCC.

Design

This was a prospective, single-blind, randomized, controlled trial.

Method

This study was conducted with approval and oversight from the University of Montana Institutional Review Board (protocol #163-22). Individuals with refractory chronic cough (RCC) in the United States were recruited for the study via social media campaigns, newspaper advertisements, flyers sent to voice and upper airway clinics, word-of-mouth, and Facebook

support groups. Participants provided informed consent online via the study website (hosted by the iTerapi ePlatform). Prior to study recruitment, participant identification numbers were sorted by a random number generator to determine grouping and then were assigned to participants based on chronological study enrollment. Participants were blinded to their group assignment. They were contacted by a member of the study team and participated in a short training phone call or HIPAA-compliant audio/video call instructing them on how to navigate the study website and access the study materials.

Intervention

The IBCST and control treatments included five weeks of content presented in weekly modules consisting of video explanations and demonstrations, supplemental text explanations, and a downloadable handout. Participants were prompted to answer a treatment adherence question at the beginning of each week to indicate whether they consistently followed the recommendations for the previous week. The participants received automated reminders via their preferred mode of communication (email or text) to complete the study questionnaires and alert them when new content was available.

The IBCST intervention included education on cough hypersensitivity syndrome and the rationale for BCST, vocal hygiene education, instruction in cough suppression strategies, functional practice of cough suppression in daily life, and implications for long-term management. The healthy lifestyle education control treatment was informed by the control treatments described in prior BCST randomized controlled trials (Chamberlain Mitchell et al., 2016; Vertigan et al., 2006) and was based on publicly available information from the Centers for Disease Control and Prevention. Topics included general education, physical activity, healthy

eating, stress management, and relaxation techniques. Control participants were provided with the opportunity to participate in the IBCST intervention after their study participation ended.

Assessments/Outcome Measures

Changes in cough-related quality of life and perception of cough severity were used to assess the efficacy of IBCST compared to the control treatment. The LCQ is a 19-item, validated, reliable, and repeatable self-report questionnaire about cough-related quality-of-life (Birring et al., 2003) and was the primary outcome measure. A higher score indicates better cough-related quality-of-life. The secondary outcome measure was the Cough Severity Visual Analog Scale (VAS) which is a 100-millimeter line with anchors of 0 "no problem" and 100 "worst possible problem" where participants place a mark to represent the severity of their current cough problem. These assessments were administered online using the iTerapi ePlatform at baseline (T0), one-week post-treatment (T1), and one-month post-treatment (T2). A change of 1.3 is considered the minimally important clinical difference on the LCQ (Raj et al., 2009) and a reduction of at least 30-millimeters is considered clinically meaningful for the Cough Severity VAS (Martin Nguyen et al., 2021).

Statistical Analyses

The original sample size goal was calculated with a power analysis (G*Power 3.1, Faul et al., 2009) and determined to be 48 participants based on a one-tailed independent samples (prepost) *t*-test with an effect size of 0.80, alpha level of .05, and power set at .85. The power level of .85 was deemed sufficient based on the only prior randomized control trial examining the efficacy of BCST that used the LCQ as a primary outcome measure (Chamberlain Mitchell et al., 2016). A large effect size of .80 was chosen as a conservative value which would be advantageous as we planned to run an analysis of covariance (ANCOVA) and not a *t*-test to

analyze LCQ score change. To account for the possible attrition rate of 16.5% reported in a previous study (Chamberlain Mitchell et al., 2016), we had a goal to recruit 56 participants. This sample target size number was modified as the study progressed due to multiple factors, including a shorter than anticipated recruitment timeline related to a funding delay, and interim analyses that showed a large difference in the primary outcome measure between groups.

Analyses were conducted using R-4.4.2 (R Core Team, 2021). Group differences in mean total LCQ and VAS scores from T0-to-T1 and T0-to-T2 were examined, accounting for T0 assessment scores using an ANCOVA. The variance in responses for both LCQ and VAS scores was very high, making it difficult to determine linearity between T0 and T1 and T2 scores. Therefore, an interaction term between the treatment group and T0 score was considered to account for the potential different treatment effects at different T0 scores. All interaction terms were not statistically significant (p = .26, p = .46, p = .95, p = .36) for LCQ at T1, LCQ at T2, VAS at T1, or VAS at T2, respectively, suggesting homogeneity of the regression slopes. Shapiro-Wilk tests suggested insufficient evidence of non-normality of residuals (p = .89, p = .09, p = .29, p = .38). Lastly, Levene's test found no evidence of error variance heterogeneity (p = .30, p = .74, p = .58, and p = .47). Thus, the basic assumptions necessary for the ANCOVA were met.

Results

Thirty-nine individuals with RCC enrolled in the study between July 2023 and June 2024. Twelve participants completed the control treatment (11 women; mean age, 60 years) and 18 completed the IBCST treatment (16 women; mean age, 62 years). One IBCST participant was lost to follow up at T2 and so was not included in T2 analyses.

Leicester Cough Questionnaire

At T1, 72% of IBCST participants achieved a meaningful improvement in LCQ total score and this increased to 76% at T2. Mean domain and total LCQ scores for both groups during each assessment period are shown in Table 1. Change in mean total LCQ scores from T0-T1 was 3.74 and 0.58, and from T0-T2 was 4.10 and 0.83, for the IBCST and control groups, respectively. ANCOVA analysis revealed mean total LCQ score changes were significantly greater in the IBCST group than in the control group from T0-to-T1 (mean difference between groups = 3.24, 95% CI = 0.72-5.76, standard error = 1.227, p = .014, ηp^2 = 0.205), and T0-to-T2 (mean difference between groups = 3.30, 95% CI = 0.286-6.32, standard error = 1.467, p=0.033, ηp^2 = 0.163).

Cough Severity Visual Analog Scale (VAS)

Mean VAS scores for both groups at each assessment period are shown in Table 1. Change in mean total VAS scores from T0-T1 was -15 and 1, and from T0-T2 was -7 and 7, for the IBCST and control groups, respectively. ANCOVA analysis revealed there was mild evidence of a larger decrease from T0-to-T1 for the IBCST group compared to the control group (mean difference between groups = -16.1, 95% CI= -32.7-0.46, Std error = 8.804, p = .056, $\eta p^2 = 0.128$), with no evidence of a difference in the mean score change from T0-to-T2 (mean difference between groups = -11.73, 95% CI = -28.53-5.06, Std. error = 8.170, p = .338, $\eta p^2 = 0.073$).

Table 1

Mean LCO and VAS Scores

		LCQ				VAS
		Physical	Social	Psych	Total	Total
					(SD)	(SD)
	T0	3.58	2.82	2.64	9.04	49
					(2.76)	(15.97)
IBCST	T1	4.62	4.03	4.13	12.78	33.94
					(3.69)	(21.32)
	T2	4.71	4.22	3.88	13.03	44.18
					(4.3)	(22.85)
	T0	3.67	2.75	2.45	8.87	49.08
					(2.76)	(22.39)
Control	T1	3.74	3.04	2.67	9.45	50.08
					(3.50)	(22.39)
	T2	3.75	3.17	2.79	9.70	56.42
					(4.29)	(23.74)

References

- Birring, S. S., Prudon, B., Carr, A. J., Singh, S. J., Morgan, M. D., & Pavord, I. D. (2003). Development of a symptom specific health status measure for patients with chronic cough: Leicester Cough Questionnaire (LCQ). *Thorax*, 58(4), 339-343. doi:10.1136/thorax.58.4.339
- Chamberlain, S. A., Garrod, R., Douiri, A., Masefield, S., Powell, P., Bucher, C., Pandyan, A., Morice, A. H., & Birring, S. S. (2015). The impact of chronic cough: a cross-sectional European survey. *Lung*, 193(3), 401-408. doi:10.1007/s00408-015-9701-2

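### The sample target was changed partly because of interim looks at the primary outcome, yet the LCQ p-values and confidence intervals are unadjusted fixed-sample figures with no caveat beside them

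*Combined protocol and SAP*

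**What the plan says.** All places are in the combined protocol and SAP.

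- **Statistical Analyses, planned size.** The target of 48 was "based on a one-tailed independent samples" t-test with effect size 0.80, alpha .05 and power .85. Allowing for 16.5% attrition, "we had a goal to recruit 56 participants".
- **Statistical Analyses, change of size.** "This sample target size number was modified as the study progressed due to multiple factors". Two are named. The first is logistical: "a shorter than anticipated recruitment timeline related to a funding delay". The second comes from the accumulating data: "interim analyses that showed a large difference in the primary outcome measure between groups". The text does not say which was decisive. It also does not give the revised target, the number or timing of the looks, how many participants each included, whether they used T1 or T2 data, what rule was applied, or any control of alpha.
- **Results.** "Thirty-nine individuals with RCC enrolled in the study between July 2023 and June 2024". Twelve control and 18 IBCST participants completed treatment, 30 in all. "One IBCST participant was lost to follow up at T2 and so was not included in T2 analyses", which leaves 29.
- **Leicester Cough Questionnaire.** The group differences in LCQ change are described as significant: 3.24 at T1 (SE 1.227, 95% CI 0.72 to 5.76, p = .014) and 3.30 at T2 (SE 1.467, 95% CI 0.286 to 6.32, p = .033). The interim looks are not mentioned here.

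**The concern.** A fixed-sample p-value and 95% interval assume that the sample size did not depend on the effect seen along the way. The document says that the target did depend on it, at least in part. Cutting a target after a favourable look gives a chance finding less opportunity to fade. The type I error then rises above its nominal level and the average estimate is too large.

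At stake is the headline claim on the primary outcome at both time points. A reader who wants to discount for the looks cannot do so, because the details needed are missing. A reader who sees only the LCQ results has no sign that a discount might be needed.

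**Working it through.** **1. Are the reported LCQ figures fixed-sample figures?** The inputs are the differences and SEs in the LCQ results. The ANCOVA has group and T0 score as terms, so residual df = n − 3. Formulae: t = difference/SE; CI = difference ± t(.975, df) × SE.

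- T1: 3.24/1.227 = 2.641 on 27 df. Two-sided p = .0136 (one-sided .0068), CI 0.722 to 5.758.
- T2: 3.30/1.467 = 2.249 on 26 df. Two-sided p = .0332 (one-sided .0166), CI 0.285 to 6.315.

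Both match the stated values within rounding, so no adjustment was applied.

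**2. How far short was the trial, and why?** Enrolment was 56 − 39 = 17 below goal. Attrition was 9/39 = 23.1% against 16.5% assumed. At the assumed rate, 39 enrolled would have given 39 × (1 − .165) = 32.6 completers. Attrition therefore explains a small part of the gap between 30 and 48, and the rest is lower enrolment.

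**3. Illustrative error rates.** The looks are not described, so every schedule here is an assumption. Simulated t-test trials (200,000 per case, 60:40 split as in 18 and 12, two-sided .05):

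| Assumed rule | Type I error | Mean estimate at true d = 0.80 |
|---|---|---|
| Single analysis at 30 (check) | 4.9% | 0.80 |
| One look at 16 to 26; p<.05 only moves the analysis from 48 to 30 | 5.6% to 6.4% | 0.83 to 0.85 (4% to 6% high) |
| Two or three analyses, stop at p<.05 | 7.8% to 11.0% | 0.85 to 0.93 |
| Five analyses, stop at p<.05 | 14.4% | 0.98 |

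**4. Would the LCQ results survive an adjustment?** Pocock-type adjusted p = P(maximum Z over the looks ≥ observed value), using |Z| for the two-sided version. Twelve schedules of two to five analyses were tried, with 29 in place of 30 for T2, and four more for T2 alone.

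- *T1, two-sided:* adjusted p .019 to .043; passes all 12.
- *T1, one-sided:* .010 to .022; passes all 11 schedules rerun.
- *T2, two-sided:* misses 12 of 16 (about .051 to .097). It passes with a single look at 22, 24 or 26 of 29 (.049, .047, .044) and with looks at 26 and 28 of 29 (.047).
- *T2, one-sided .05, the basis used for sizing:* passes all 11 schedules rerun: .022 to .028 with two analyses, .029 to .036 with three, .041 with four, and narrowly (.049) with five.

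Full-information O'Brien-Fleming final levels for two to five equal looks are .048, .045, .043 and .041 (two-sided). T1 and T2 both pass.

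If the analysis is instead treated as an early stop against 48, O'Brien-Fleming-type spending at information fraction t allows 2(1 − Φ(z(1−a/2)/√t)). The one-sided .05 level uses a = .05; the two-sided level is twice the value at a = .025.

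| | Two-sided level | Observed | One-sided level | Observed |
|---|---|---|---|---|
| T1, t = 30/48 | .0092 | .0136, misses | .0132 | .0068, passes |
| T2, t = 29/48 | .0079 | .0332, misses | .0117 | .0166, misses |

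**The case against.** The strongest reply is that the looks may have done no harm. The document names a funding-related timeline as a cause and describes no significance-based stopping rule. It also shows more attrition than planned, so 30 need not have been a chosen stopping point. This stands. If funding alone ended recruitment, the looks inflated nothing. But the document lists both causes and only the authors can say which decided the matter.

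A second reply is that the looks are disclosed, in the section just before the results. That also stands, and rules out any suggestion of concealment. Saying that looks took place does not, however, qualify the inference that follows or supply the details needed to judge it.

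A third reply is that the larger error rates are hypothetical. This is fair. The 8% to 14% range rests on stop-at-p<.05 rules found nowhere in the document, and some schedules include analyses at 40 or 48 that were never reached. The case closest to the text, a look that only changes the target, gives about 6%.

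A reader might go further and infer that recruitment was stopped for significance, or that the T2 result fails once the looks are allowed for. The document does not support the first. The calculations do not support the second: T2 passes with late looks, under full-information O'Brien-Fleming, and under every one-sided Pocock-type schedule rerun.

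**Conclusion.** The concern holds as a gap in inference and reporting. The target change was partly data-driven by the document's own account, and the LCQ p-values and intervals take no account of that. They can be read only as nominal. Confidence is high in that statement; it does not extend to the size of any inflation, which cannot be computed. That the target was reduced is itself an inference from 39 enrolled against 56, since the revised figure is not stated.

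Conditional on assumed looks, T1 is fairly robust: of the settings tried, it misses only the two-sided O'Brien-Fleming-type early stop against 48. For T2 the answer turns on sidedness, schedule and boundary, so it should be presented neither as secure nor as overturned.

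**What to change.** 1. In the LCQ results, label the p-values and 95% CIs as nominal and unadjusted for a partly data-driven change in sample size. Reword the significance claim to match.
2. In Statistical Analyses, state the number and timing of the looks, the number of participants and the time point (T1 or T2) used in each, what each look decided, the revised target, and what ended recruitment. If funding alone ended it, saying so would largely answer the concern.
3. Optional: if the actual looks can be reconstructed, add adjusted p-values, CIs and a bias-adjusted estimate as a sensitivity analysis, stating the sidedness. If they cannot, a post hoc range would mostly restate its own assumptions.

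The first two steps need wording and disclosure only, with no new participants or data. The price is a less firm claim, mainly at T2.

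### The LCQ comparisons use 30 (T1) and 29 (T2) of 39 enrolled, apparently all allocated; nine have no stated arm or reason, and no missing-data method or sensitivity analysis is described

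*Combined protocol and SAP*

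**What the plan says.** Method says that, before recruitment, "participant identification numbers were sorted by a random number generator to determine grouping and then were assigned to participants based on chronological study enrollment". Neither the allocation ratio nor the number allocated to each arm is given.

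Results says "Thirty-nine individuals with RCC enrolled in the study between July 2023 and June 2024", then "Twelve participants completed the control treatment (11 women; mean age, 60 years) and 18 completed the IBCST treatment", and adds: "One IBCST participant was lost to follow up at T2 and so was not included in T2 analyses".

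Statistical Analyses names an ANCOVA adjusted for the T0 score and reports checks of slopes, residual normality and error variance. It names no analysis population, missing-data method or sensitivity analysis. Attrition appears only in the sample-size paragraph: "To account for the possible attrition rate of 16.5% reported in a previous study", the recruitment goal was set at 56.

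The Leicester Cough Questionnaire section gives the T1 result as "mean difference between groups = 3.24, 95% CI = 0.72-5.76, standard error = 1.227, p = .014" and the T2 result as "mean difference between groups = 3.30, 95% CI = 0.286-6.32, standard error = 1.467, p=0.033", with partial eta squared of 0.205 and 0.163. On responders it says: "At T1, 72% of IBCST participants achieved a meaningful improvement in LCQ total score and this increased to 76% at T2".

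**The concern.** The stated aim is efficacy against a randomised control. Randomisation protects the comparison of everyone allocated. It does not fully protect a comparison of those who finished, because finishing may depend on the arm and on how the cough responded.

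Nine of the 39 people drop out of the account between enrolment and the analysed sample. Without their arm, a reader cannot tell whether loss was balanced or heavily one-sided. Without a sensitivity analysis, a reader cannot tell how much it would matter. This bears on the primary outcome, and most on T2, where the lower confidence limit is 0.286 points.

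The responder sentence raises a smaller, related matter. It reads as further gain at one month, although the denominator changed between the two visits.

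**Working it through.** **1. How many people are in the published ANCOVAs?** The inputs are the difference, standard error and partial eta squared in the Leicester Cough Questionnaire section. With t = difference/SE, residual df = t² × (1 − η)/η, and N = df + 3 (intercept, group, T0 score).

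- T1: t = 3.24/1.227 = 2.641; t² = 6.973; df = 6.973 × 0.795/0.205 = 27.04. So N = 30, and p on 27 df is .0136 (published .014).
- T2: t = 3.30/1.467 = 2.249; t² = 5.060; df = 5.060 × 0.837/0.163 = 25.98. So N = 29, and p on 26 df is .0332 (published 0.033).

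With N = 39, partial eta squared would be 0.162 at T1 and 0.123 at T2, which does not match. The analysed sets are the 12 + 18 completers, then 12 + 17.

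**2. How many are absent?** If all 39 were allocated: 9/39 = 23.1% at T1 and 10/39 = 25.6% at T2.

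**3. What could loss by arm look like?** Arm totals are not given. The completer counts allow control/IBCST splits from 12/27 to 21/18. Loss at T1 is (c − 12)/c for control and (i − 18)/i for IBCST.

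| Split (control/IBCST) | Control loss | IBCST loss |
|---|---|---|
| 19/20 | 7/19 = 36.8% | 2/20 = 10.0% |
| 20/19 | 8/20 = 40.0% | 1/19 = 5.3% |
| 16/23 | 4/16 = 25.0% | 5/23 = 21.7% |

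The document therefore allows both strongly unequal and roughly balanced loss.

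**4. One illustrative sensitivity scenario.** Suppose missing IBCST participants changed as controls did, and missing controls changed as observed controls did. The effect becomes the published difference × observed IBCST/allocated IBCST. Two conventions for the standard error are shown:

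- Held: the published SE and df, which give no credit for the added people.
- Recomputed: residual SD = 1.227/√(1/12 + 1/18) = 3.29 at T1 and 1.467/√(1/12 + 1/17) = 3.89 at T2. Multiplied by √(1/19 + 1/20) = 0.320, these give SEs of 1.055 and 1.246 on 36 df. This is optimistic, because it treats the missing scores as if they had been observed.

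| Visit, split | Effect | p, SE held | p, SE recomputed |
|---|---|---|---|
| T1, 19/20 | 3.24 × 18/20 = 2.92 | .025 | .009 |
| T1, 20/19 | 3.24 × 18/19 = 3.07 | .019 | .006 |
| T2, 19/20 | 3.30 × 17/20 = 2.80 | .067 | .031 |
| T2, 20/19 | 3.30 × 17/19 = 2.95 | .055 | .023 |

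These are approximations from summary data. If more of the nine were in IBCST, the effect in this scenario would shrink further.

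**5. Responders.** With 18 people, only 13/18 = 72.2% rounds to 72%. With 17, only 13/17 = 76.47% rounds to 76%. The count is 13 at both visits and the denominator fell by one. If missing IBCST participants count as non-responders, both visits give 13/20 = 65.0% or 13/19 = 68.4% at the near-equal splits.

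**The case against.** The strongest reply is that the completer basis is largely visible. Enrolment and completer counts are printed next to each other, and the T2 exclusion is stated outright, so a reader can subtract and infer complete-case handling. That stands. What subtraction cannot recover is the arm, reason and outcome status of the nine, or how sensitive the results are to them.

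A second reply is that enrolled need not mean allocated. Identification numbers carried a pre-set group and were given in enrolment order, which points to all 39 having an arm, but the document does not say so. The loss rates depend on that inference.

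A third is that, if the nine have only T0 scores, imputing from arm and T0 score would essentially return the present estimate. This is correct, and it is why a sensitivity analysis with an explicit departure from that assumption is needed.

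A fourth is that the scenarios are hypothetical and the T2 answer changes with the standard error used. This is also correct. They show that the question is open at T2, not how it would be answered.

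On responders, the proportion did literally rise, so the sentence is not false. A reader might go further and infer that nobody became a responder after T1. The document does not support that. If the person lost at T2 had been a T1 responder, the remaining 17 went from 12 to 13. Only the unchanged total is known.

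**Conclusion.** The concern holds as a gap in analysis and reporting that should be fixed. Both LCQ results are completer estimates, from 30 and 29 people. If all 39 were allocated, 23.1% and 25.6% are absent, above the 16.5% foreseen. Nothing stated lets a reader judge the effect of the nine earlier losses.

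At near-equal arms, which is an assumption, and with missing IBCST participants behaving as controls, T1 is 2.9 to 3.1 points and stays below p = .05 under either convention. T2 is 2.8 to 2.95 points and falls on either side of .05 depending on the convention. T2 is the more fragile of the two.

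A reader might infer that controls dropped out far more often, that the benefit is overstated, or that the T2 finding is void. None of these follows: the losses by arm are not reported, roughly balanced loss is also possible, and no direction of bias can be shown.

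**What to change.** - Analyse participants as allocated, using every T1 and T2 score held, including any from people who did not complete treatment.
- Add one tipping-point or reference-based sensitivity analysis at T1 and T2, with its assumption stated. If the nine have only T0 scores, say so and let this analysis carry the weight.
- Report allocation, completion and reasons for loss by arm, and state whether all 39 were allocated.
- Label the present ANCOVA a completer analysis where the Leicester Cough Questionnaire section reports a significant group difference.
- Give responders as counts with denominators (13/18, 13/17, and over those allocated) rather than as an increase.

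The cost is a participant-flow table and one re-analysis from records the study should already hold. The downside is reliance on a missing-data assumption that cannot be verified, and possibly a smaller or less certain effect.

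### The stated one-month IBCST change in VAS (-7) differs from Table 1 (-4.82), cannot hold together with Table 1 and the T2 ANCOVA line, and sits beside two other inconsistent VAS figures

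*Combined protocol and SAP*

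**What the plan says.** All the figures are in the Results of the combined protocol and SAP.

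- The VAS subsection gives the unadjusted changes: "Change in mean total VAS scores from T0-T1 was -15 and 1, and from T0-T2 was -7 and 7", for IBCST and control in that order.
- The same subsection gives the T2 comparison: "mean difference between groups = -11.73, 95% CI = -28.53-5.06, Std. error = 8.170, p = .338", with partial eta-squared 0.073. For T1 it gives -16.1, CI -32.7 to 0.46, SE 8.804, p = .056 and partial eta-squared 0.128.
- The Table 1 row for IBCST at T0 reads "3.58 2.82 2.64 9.04 49"; the last entry is the VAS mean (SD 15.97). The other IBCST VAS means are 33.94 at T1 and 44.18 at T2. Control has 49.08, 50.08 and 56.42. The table gives no n per cell.
- Twelve control and 18 IBCST participants completed treatment. On follow-up the Results say: "One IBCST participant was lost to follow up at T2 and so was not included in T2 analyses".
- Statistical Analyses describes the model as "accounting for T0 assessment scores using an ANCOVA".

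**The concern.** Three of the four stated VAS changes can be read off Table 1; the fourth, the IBCST change at one month, cannot. The gap of about 2 mm is too large for rounding. The missing participant is the natural explanation, but it has a consequence that can be tested. If the 17 people analysed started higher than 49, the baseline-adjusted difference has to move accordingly, and the reported one does not.

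VAS is the secondary outcome, and T2 is the only VAS reading later than one week after treatment. The figure therefore shapes how a reader judges whether the gain lasts. Against the stated T1 change of -15, a change of -7 keeps 7/15 = 47% of the gain; -4.82 keeps 32%. Anyone extracting change scores for a synthesis would take a between-group gap of -7 - 7 = -14, against -4.82 - 7.34 = -12.16 from Table 1.

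**Working it through.** **1. Changes from Table 1**

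| | Table 1 | Stated |
|---|---|---|
| IBCST T0-T1 | 33.94 - 49 = -15.06 | -15 |
| Control T0-T1 | 50.08 - 49.08 = +1.00 | 1 |
| Control T0-T2 | 56.42 - 49.08 = +7.34 | 7 |
| IBCST T0-T2 | 44.18 - 49 = -4.82 | -7 |

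If the printed 49 is itself rounded (48.5 to 49.5), the last change still lies between -4.32 and -5.32.

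**2. Can the missing participant explain -7?** Take T0 as the mean of 18 and T2 as the mean of 17. A change of -7 needs a T0 mean in the 17 of 44.18 + 7 = 51.18. The lost participant's T0 is then 18 × 49 - 17 × 51.18 = 882 - 870.06 = 11.94 mm, or (11.94 - 49)/15.97 = -2.3 SD. Over the rounding range -6.5 to -7.5 it is 20 to 3 mm (-1.8 to -2.9 SD). That is extreme but possible.

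**3. Does -7 then fit the ANCOVA estimate?** With common slope b and IBCST baseline mean x in the 17:

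adjusted difference = (44.18 - 56.42) - b(x - 49.08) = -12.24 - b(x - 49.08).

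At x = 51.18 the baseline gap is +2.10. To reach -11.73, b = (-12.24 + 11.73)/2.10 = -0.24 (range -0.32 to -0.20 over rounding). Any non-negative slope gives -12.24 or something more negative.

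**4. What slope does the reported SE imply?** Inputs are SE 8.170, n = 17 and 12, 26 df and the Table 1 SDs.

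- Within-group T2 sum of squares: 16 × 22.85² + 11 × 23.74² = 14,553.
- Within-group T0 sum of squares, with the lost participant removed: 17 × 15.97² - (11.94 - 49)² × 18/17 + 11 × 22.39² = 2,881 + 5,514 = 8,396.
- Residual variance: 8.170²/(1/17 + 1/12 + 2.10²/8,396) = 467.8.
- Within-group R²: 1 - 26 × 467.8/14,553 = 0.164.
- |b| = sqrt(0.164 × 14,553/8,396) = 0.53.

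The adjusted difference would then be -12.24 - 0.53 × 2.10 = -13.4 with a positive slope, or -11.1 with a negative one. Over the rounding range |b| is 0.51 to 0.56 and the results are -13.1 to -13.7, or -10.8 to -11.4. None of these is -11.73.

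**5. Which changes would fit?** Two do, depending on the sign of the slope:

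- slope +0.50, x about 48.06, change -3.9: -12.24 + 0.50 × 1.02 = -11.73;
- slope -0.50, x about 50.10, change -5.9: -12.24 + 0.50 × 1.02 = -11.73.

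Neither rounds to -7.

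**6. Rest of the VAS paragraph**

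- T2: t = -11.73/8.170 = -1.44 on 26 df, so p = .163, not .338. The CI half-width gives SE 8.17, and t²/(t² + 26) = 0.073, the stated partial eta-squared. The estimate, SE, CI and effect size agree with each other; only the p-value does not.
- T1: the CI half-width is (0.46 + 32.7)/2 = 16.58. Divided by the t quantile 2.052 on 27 df, it gives SE 8.08, p = .057 and partial eta-squared 0.128, which agree with the stated .056 (to rounding) and 0.128. The printed 8.804 would give p = .079 and 0.110. It also implies a residual SD of 8.804/sqrt(1/18 + 1/12) = 23.6, above the pooled T1 SD of about 21.7 and hence a negative within-group R² (-0.14), which is impossible.

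**The case against.** The best defence is the change of denominator. The document says that one IBCST participant is absent from the T2 analyses, and Table 1 does not claim a common n. The LCQ shows the same pattern: the stated T2 changes are "from T0-T2 was 4.10 and 0.83, for the IBCST and control groups, respectively", while Table 1 gives 13.03 - 9.04 = 3.99 for IBCST and exactly 0.83 for control. Changes computed on the 17 would explain this. They imply a lost-participant T0 LCQ of about 10.9, better than the group mean of 9.04, and a low T0 VAS would likewise mean a milder cough. This stands: a reader might infer that -7 is irreconcilable with Table 1, but Table 1 alone does not exclude it. What the defence does not do is bring -7 into line with -11.73 and SE 8.170. For the LCQ it does work: a T0 mean of 8.93 in the 17 and a slope of 0.5 return the reported 3.30.

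A second objection is that the ANCOVA line is a poor yardstick, since the paragraph has a wrong p-value and a wrong SE, and the control VAS SD is printed as 22.39 at both T0 and T1, possibly a copying slip. That also stands, and it is why the check cannot single out -7 as the error. Nor is -14 against -11.73 a fault in itself, because an adjusted difference need not equal a difference in raw changes. The conflict appears only through the slope and SE.

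Third, little turns on it. The outcome is secondary, the T2 CI covers zero, and both -5 and -7 are far from the 30 mm reduction that the document treats as meaningful. This is correct, and it limits the point to the accuracy of reported results.

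**Conclusion.** The point holds as a joint inconsistency. The stated -7 differs from Table 1 by about 2.2 mm. The one explanation that the document offers needs an extreme baseline in the lost participant and still leaves -7 at odds with the T2 ANCOVA. This rests on three assumptions: the printed SDs are right, the Table 1 T0 mean covers all 18 IBCST participants, and the ANCOVA used the same 17 and 12 people. At least one of -7, the Table 1 VAS means or SDs, or the T2 ANCOVA line is therefore wrong.

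A reader might infer that the one-month improvement is overstated and was really about -3.9. That is plausible but not shown: it needs a positive slope and an error-free ANCOVA line, and the documents establish neither. T2 is also not the only post-treatment VAS reading, since T1 was taken one week after treatment.

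The other two discrepancies are firmer, because each compares one figure with several companions: p = .338 should be about .163, and SE 8.804 about 8.08. The conclusion that the VAS shows no T2 difference does not change on the figures given.

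**What to change.** - Recompute the T0-T2 VAS change on the 17 IBCST participants in the T2 analysis.
- State n for each cell of Table 1, and add the T0 mean and SD of those 17, so that the change and the adjusted difference rest on one visible baseline.
- Re-run both VAS ANCOVAs and print the estimate, SE, CI, p and partial eta-squared from a single output.
- Correct whichever of -7, the Table 1 VAS entries (including the repeated control SD of 22.39), -11.73 with 8.170, p = .338 and SE 8.804 prove wrong.

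The cost is one re-run on data in hand, a corrected paragraph and an added table row. The only downside is that the one-month VAS change may come out less favourable.
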